3.1.9 Methods: Data collection, management, and analysis

Data collection is done by reviewing the electronic medical records of participants. No additional tests or interventions are undertaken other to those that are considered as standard of care. Collected data can be found in the EHS-registry as mentioned under 1.2.20 and 1.2.21. Additional data (if applicable) will be supplied within the final report. All relevant data regarding the outcome measures explained under 1.2.16 and 1.2.17 will be collected for all enrolled participants.

Uncoded data is entered and stored to files only accessible to members of the primary sponsor (1.2.2). Data quality will be regularly checked by contributor 1.

A biostatistician was consulted for advice regarding statistical analysis. Statistical analysis was performed by contributor 1. JASP [9] was used for the majority of statistical analysis, Vassarstats [10] was used to calculate Fisher's exact tests on 3 x 2 contingency tables, XLSTAT [11] was used to create Kaplan-Meier curves.

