1.2.10 Inclusion Criteria

Group 1 (eTEP):

- Patients who underwent an eTEP procedure in our center
- Preoperative existence of one or more midline abdominal wall hernias
- Preoperative existence of rectus abdominis diastasis

Group 2 (Rives-Stoppa, control group):

- Patients who underwent an open Rives-Stoppa (midline repair with sublay mesh) in our center

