1.2.12 Study Type

Single-center, observational study.

Non-randomized allocation:

- Group 1 (eTEP): First 30 patients who meet the inclusion criteria and do not exhibit any of the exclusion criteria will be investigated. The option for endoscopic eTEP repair, if feasible, is given preoperatively as a standard for the treatment of symptomatic midline abdominal wall hernias with concomitant rectus abdominis diastasis as an alternative to open Rives-Stoppa mesh repair. The modality of operative treatment is made in cooperation with the patient.
- Group 2 (Rives-Stoppa, control): Thirty patients will be selected out of all patients who underwent an open Rives-Stoppa (midline repair with sublay mesh) in our center and who do not meet any of the exclusion criteria. Patient selection will consist of matching to patients in group 1 according to gender and age (e.g. a male patient in group 1 will be matched to a male patient (group 2) out of our records

who underwent an open Rives-Stoppa repair and whose age most closely resembles the age of the matched patient in group 1).

Masking: None.

Assignment: Two-group, parallel.

Purpose: Comparing two routinely used interventions for the treatment of midline abdominal wall hernias with rectus abdominis diastasis.

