1.2.20 Summary of Results

Date of posting of results summaries: December 26, 2022 (within study protocol).

Date of the first journal publication of results: Not yet achieved.

[figure not shown]
URL: Not (yet) applicable.

Baseline characteristics:

- Group 1 (eTEP): EHS Registry: BEGZ, BEHA, BEHB, BEJR, BEJS, BEJT, BEJW, BEJX, BEJZ, BEKA, BEKB, BEKC, BEKG, BEKH, BEKI, BEKJ, BEKK, BEKK, BEKM, BELE, BELF, BELG, BELH, BELI, BELJ, BELK, BELL, BEOD, BETJ, BETK.
- Group 2 (Open RS): EHS Registry: BELN, BELO, BELQ, BELR, BELS, BELT, BELU, BELV, BELV, BELY, BEOF, BEOH, BEOO, BEPV, BEPX, BEPY, BEPZ, BEQA, BEQF, BEQG, BEQJ, BEQK, BEQQ, BEQR, BEQS, BEQT, BEQV, BEQX, BETN, BETO.

Participant flow (see also participant flowchart on next page):

Date	Group 1	Group 2
June 9, 2022	23 participants	23 participants
June 13, 2022	24 participants	24 participants
June 17, 2022	25 participants	25 participants
June 20, 2022	26 participants	26 participants
June 21, 2022	27 participants	27 participants
July 11, 2022	28 participants	28 participants
August 30, 2022	30 participants	30 participants

Adverse events:

- Three conversions were needed in group 1 (eTEP) because no adequate visualization could be achieved (1 participant) or because the diastasis was deemed to large to be appropriately closed endoscopically (2 participants)
- Observed complicationa according to the Clavien-Dindo (CD) classification [3]:
 During hospital stay in the eTEP group: 1x CD I, 12x CD II.

 During hospital stay in the Open RS group: 4x CD I, 10x CD II, 4x CD IIIb.

 After discharge until 30 days in the eTEP group: 5x CD I, 1x CD II, 2x CD IIIa, 1x CD IIIb.

 After discharge until 30 days in the Open RS group: 5x CD I, 1x CD II, 5x CD IIIa, 4x CD IIIb.

Outcome measures: See brief summary.

URL protocol files: Not applicable.

Brief summary:

- Median length of hospital stay was longer in the open RS group.
- Median duration of patient-controlled analgesia was longer in the open RS group.
- Switch to only oral analgesics took longer in the open RS group.
- No significant difference in 'comparable parameter'* for postoperatively administered analgesics irrespective of PCA between both groups.
- No significant difference between the presence of prescription opioids at discharge.
- Median duration of surgery (skin-to-skin time) was significantly shorter in the open RS group.
- Need for drainage (postoperative drain inserted during primary surgery) was significantly greater in the open RS group.

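### Controls are matched on gender and age only, and no adjustment or balance check for hernia characteristics or patient risk is stated, so confounding may bias the comparison of stay and analgesic use

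*Protocol*

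**What the plan says.** **Allocation.** Protocol 1.2.12 describes non-randomised allocation. "The option for endoscopic eTEP repair, if feasible, is given preoperatively as a standard", and "The modality of operative treatment is made in cooperation with the patient".

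**Control of confounding in the design.** The same section draws the 30 controls from all eligible open Rives-Stoppa patients at the centre: "Patient selection will consist of matching to patients in group 1 according to gender and age", taking the closest age. No other matching variable is named.

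**Eligibility.** Under 1.2.10, Group 1 needs both a midline hernia and a rectus diastasis. The only entry condition for Group 2 is "Patients who underwent an open Rives-Stoppa (midline repair with sublay mesh) in our center".

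**Analysis.** Section 3.1.9, in the past tense, states that "JASP [9] was used for the majority of statistical analysis", that "Vassarstats [10] was used to calculate Fisher's exact tests on 3 x 2 contingency tables", and that XLSTAT produced the Kaplan-Meier curves. It names no test or model for length of stay or for the analgesic measures. It mentions no regression, stratification, propensity score or matched-pair method.

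**Results and baseline data.** Section 1.2.20 reports a longer median stay after open repair, with further crude comparisons. Under baseline characteristics it gives registry record codes only. On the data themselves, 3.1.9 says: "Collected data can be found in the EHS-registry as mentioned under 1.2.20 and 1.2.21".

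**The concern.** Section 2.1.3 calls this a superiority cohort study, and the first posted result is longer stay after open repair. Hernia size, primary versus incisional or recurrent hernia, BMI and general patient risk could each plausibly affect stay, drain use and analgesic need. A feasibility condition on eTEP can also make them differ between the groups. Matching on gender and age removes none of that, except as far as these factors follow gender and age.

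The gap is also visible in the completed work. The wording on statistical analysis was extended in version 3, dated after the actual completion date, and it describes analyses already done. With no baseline table and no adjusted estimate posted, a reader cannot tell how much of the difference in stay belongs to the technique and how much to case mix.

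**Working it through.** **1. Nothing to reproduce.** The protocol gives 30 per group (1.2.14) without alpha, power, effect size or SD, and it gives no estimate of imbalance. Everything below is for scale and rests on stated assumptions.

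**2. What the design and stated analysis control.**

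| Factor | Matching (1.2.12) | Same entry rule in both groups (1.2.10) | Adjustment stated (3.1.9, 1.2.20) |
|---|---|---|---|
| Gender, age | yes | – | no |
| Presence of diastasis | no | no, Group 1 only | no |
| Hernia or diastasis size | no | no | no |
| Patient risk (e.g. BMI, ASA class) | no | no | no |

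**3. Size of a possible bias.** Assume a normal outcome, no true treatment effect, and one confounder that differs by D SD between groups and has within-group correlation r with the outcome. Then:

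- crude bias, in outcome SDs = D × r
- noncentrality of the two-sample t-test = bias / √(2/30) = bias × √15
- false-positive rate = probability that a noncentral t with 58 df falls outside the two-sided 5% limits

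Example: D = 0.5 and r = 0.3 give a bias of 0.15; 0.15 × 3.873 = 0.58; the rate is 8.8%.

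Simulation (8,000 runs per setting) against the formula:

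| D | r | D × r | Crude rate, simulated | Crude rate, formula |
|---|---|---|---|---|
| 0.3 | 0.3 | 0.09 | 6.3% | 6.4% |
| 0.5 | 0.3 | 0.15 | 9.1% | 8.8% |
| 0.8 | 0.3 | 0.24 | 14.8% | 15.0% |
| 1.0 | 0.3 | 0.30 | 22.3% | 20.8% |
| 0.3 | 0.5 | 0.15 | 8.7% | 8.8% |
| 0.5 | 0.5 | 0.25 | 15.4% | 15.9% |
| 0.8 | 0.5 | 0.40 | 33.6% | 33.2% |
| 1.0 | 0.5 | 0.50 | 48.0% | 47.8% |

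The two agree to within 1.5 percentage points. With linear adjustment for the confounder, the simulated bias is about zero and the rate is 4.6% to 5.2% in every setting. That is the ideal case, in which the confounder is measured and correctly modelled.

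**4. Comparison with detectable effects.** At 30 per group, 80% power at two-sided 5% needs a difference of √(2/30) × (1.960 + 0.842) = 0.258 × 2.802 = 0.72 SD. Under the assumed range, a bias of 0.09 to 0.50 SD is about one eighth to two thirds of that (0.09/0.72 = 0.13; 0.50/0.72 = 0.69).

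**5. Direction.** The feasibility condition could send harder cases to open repair, which would flatter eTEP. The entry rules could do the opposite: every eTEP patient has a diastasis and a control need not, which would work against eTEP. The protocol does not settle which dominates.

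**The case against.** Section 3.1.9 lists software; it is not a model specification. Most analyses were run in JASP with methods unnamed, and covariates and balance tables are often left to an analysis plan, which is not at hand. A reader might infer that the primary outcomes were analysed crudely and the registry data left unused. The text does not support that: it shows that no adjustment is stated or reported, not that none was done. Nor is the Fisher sentence tied to a primary outcome; length of stay is measured in days. This part of the objection stands and limits the claim.

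A reader might also infer from the conversions, two of them "because the diastasis was deemed to large to be appropriately closed endoscopically (2 participants", that lesion size decided who received which operation. These happened within the eTEP group. They show that some large diastases were assigned to eTEP, not that size steered the choice beforehand. In addition, controls are drawn from past records with no date limit stated, while eTEP began at the centre in September 2021, so some controls may never have faced the choice.

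Finally, no imbalance is shown, and the registry variables are not listed. Both are true, so the point has to be put as a risk. They do not remove it. The section describes finished work, results are posted from it, and neither gives the baseline comparison that would let a reader judge the risk.

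**Conclusion.** The point holds as a risk of confounding that the protocol neither controls nor lets the reader assess. Allocation was not random, matching covers gender and age only, the entry rules differ on diastasis, and no adjusted or pair-respecting estimate is stated. The comparison of stay and analgesic use may be biased in either direction. It would go too far to say that differences in lesion size do pass into the primary outcomes, or that the longer stay after open repair is explained by case mix.

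The illustrative false-positive rate of about 6% to 48% rests wholly on assumed imbalances (0.3 to 1.0 SD) and correlations (0.3 to 0.5). It also assumes a t-test on a normal outcome, which the protocol does not name. It shows that moderate confounding would matter at 30 per group, not that it occurred. The change is worth making before journal publication, which 1.2.20 records as not yet achieved.

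**What to change.** In 3.1.9 and the final report:

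- **Baseline table.** Show pre-operative characteristics by group with standardised differences.
- **Adjusted estimate beside the crude one**, for length of stay and each analgesic measure, respecting the matched pairs (for example a pair random effect or pair-clustered standard errors). For stay, a proportional-odds model would serve, or a regression on log(stay + 1), since stay counts from day zero and plain log is undefined for a same-day discharge.
- **Few covariates.** Use age, gender and about three pre-operative variables recorded in both groups, for example hernia defect width, primary versus incisional or recurrent, BMI or ASA class. The protocol does not list the recorded fields, so availability in the registry or medical records must be confirmed first.
- **Diastasis width only with overlap.** If many controls have no diastasis, adjusting for its width is extrapolation.
- **Labelling.** Call the adjusted analysis post hoc, because results were posted in December 2022, and word the conclusion on stay as an association subject to residual confounding.

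Cost: no new patients. It takes a check of the records, a modest analysis and about 5 degrees of freedom from 60 patients. Values may be missing, and unmeasured confounding remains.

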1.2.14 Sample Size

Planned:

- Group 1 (eTEP): 30 participants
- Group 2 (Rives-Stoppa, control): 30 participants

Actual:

- Group 1 (eTEP): 30 participants
- Group 2 (Rives-Stoppa, control): 30 participants

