2.1 Introduction

2.1.1 Background and Rationale:

Extended view totally extraperitoneal prosthesis (eTEP) repair is a fairly new, up-and-coming technique as a treatment option for ventral abdominal wall hernias. The endoscopic eTEP approach has been proven to be a feasible approach [4, 5]. Our center recently started offering this treatment option from September 7, 2021 (first performance of the eTEP surgery within our center) onwards as a minimally invasive alternative to an open Rives-Stoppa [6] repair. A quick search revealed some comparisons of eTEP with IPOM [7], or comparisons between robotic and endoscopic eTEP [8], but little or no information could be found about comparisons between endoscopic (non-robot-assisted) eTEP and open Rives-Stoppa repair. Since the endoscopic eTEP repair and the open Rives-Stoppa repair both consist of a retromuscular mesh placement, and the endoscopic eTEP procedure is offered as a minimally invasive alternative to an open Rives-Stoppa repair in our center, an objective comparison between the two of them seemed logical.

2.1.2 Objectives:

To compare the outcomes of endoscopic eTEP repair versus open Rives-Stoppa repair in terms of length of hospital stay, postoperative pain management and complications.

2.1.3 Trial Design:

Partially retrospective, partially prospective, two-group, parallel, observational, superiority cohort study with an allocation ratio of 1:1.

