3.1.8 Methods: Assignment of interventions

Not applicable (not a controlled trial). No sequence generation, allocation concealment or blinding were applied. Matching of the control group is elaborated under 1.2.12. Participants are enrolled by one of three surgeons listed under 1.5 as contributor 2, 3 and 4. Matching of participants and (retrospective) creation of the control (Rives-Stoppa) group is done by contributor 1.

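### Does Fisher's exact test on 3 x 2 tables misanalyse a control group that was matched 1:1 on gender and age?

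*Protocol*

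**What the plan says.** The control group is built by individual matching. Protocol section 1.2.12 states: "Patient selection will consist of matching to patients in group 1 according to gender and age". Its example takes a record of the same gender "whose age most closely resembles the age of the matched patient in group 1". Section 3.1.8 adds: "Matching of participants and (retrospective) creation of the control (Rives-Stoppa) group is done by contributor 1". Section 2.1.3 calls the study a "superiority cohort study with an allocation ratio of 1:1". Section 1.2.14 gives "Group 1 (eTEP): 30 participants" and the same number of controls, hence 30 pairs.

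The statistical text in section 3.1.9 is a short account of which program did what, after advice from a biostatistician:

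- "JASP [9] was used for the majority of statistical analysis", with no test named;
- VassarStats for Fisher's "exact tests on 3 x 2 contingency tables", with no variable named;
- XLSTAT, which "was used to create Kaplan-Meier curves", with no test named.

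The protocol gives no significance level and no within-pair correlation, and nowhere says whether any analysis uses the pairs. Only the protocol was available; a separate statistical analysis plan may exist.

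**The concern.** Fisher's exact test on a group-by-category table treats the 60 patients as independent. It uses neither the pairs nor the two matching variables. A reader who sees individual matching in 1.2.12 and then an independent-samples test as the only named test in 3.1.9 will suspect that the design was ignored in the analysis.

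The usual cost is lost sensitivity. If outcomes within a pair are positively correlated, an unpaired test overstates the variance of the group difference. A true difference would then be reported as non-significant somewhat too often. Section 1.2.20 does report non-significant comparisons (analgesic use, opioid prescription at discharge), so the question deserves an answer.

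**Working it through.** **1. What the text establishes.** Section 3.1.9 assigns Fisher's 3 x 2 tests to one program and does not say whether they compare outcomes or baseline descriptors. If they are baseline descriptors, nothing needs re-analysis. The bulk of the analysis was done in JASP with unnamed tests, which may be paired or unpaired. So the text shows an independent-samples test on unidentified tables, and does not show a matched outcome being misanalysed.

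**2. Direction, if the tables are outcomes.** Patients are matched across treatment groups, not on outcome. With close matching, the unpaired contrast is therefore not biased by the matching; only its variance is affected. With within-pair correlation r, the true variance of the difference is (1 − r) times what an unpaired test assumes. For a 1-df test at nominal two-sided 5% (assumed), the actual size is 2Φ(−1.96/√(1 − r)). This gives 5.0, 4.4, 3.9 and 2.8% at r = 0, 0.05, 0.10 and 0.20. The effect is conservative for r ≥ 0.

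**3. Plausible r.** The documents give none. Pairs are matched on gender and age only, so the r that matching creates cannot exceed the share of outcome variance those two explain, and nearest-age matching lowers it further. A range of 0 to 0.2 on a latent scale is assumed as plausible.

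**4. Size for a 3 x 2 table.** Two simulations of 30 pairs compared the exact Fisher test with the paired Stuart-Maxwell test, two-sided 5%. All category shares are assumptions.

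- A: 10,000 studies per setting; null 50/30/20% in both groups; alternative 50/30/20% v 80/15/5%.
- B: 20,000 studies per setting; null 60/25/15% in both groups; alternative 70/20/10% v 35/35/30%.

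| Latent r | 0 | 0.05 | 0.10 | 0.20 |
|---|---|---|---|---|
| A: type I error, Fisher | 4.5% | 4.6% | 4.3% | 3.6% |
| A: type I error, paired | 4.4% | 4.6% | 4.6% | 4.6% |
| A: power, Fisher | 60.7% | 60.1% | 60.6% | 60.0% |
| A: power, paired | 58.1% | 58.9% | 60.4% | 62.8% |
| B: type I error, Fisher | 4.6% | 4.8% | 4.0% | 3.7% |
| B: type I error, paired | 4.3% | 4.6% | 4.4% | 4.4% |
| B: power, Fisher | 70.4% | 71.0% | 70.9% | 71.6% |
| B: power, paired | 67.8% | 69.4% | 70.7% | 74.8% |

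Paired minus Fisher power:

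- A: 58.1 − 60.7 = −2.6 points at r = 0; 62.8 − 60.0 = +2.8 at r = 0.2.
- B: 67.8 − 70.4 = −2.6 points at r = 0; 74.8 − 71.6 = +3.2 at r = 0.2.

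The sign changes within the plausible range. A clear advantage for pairing appears only at higher r: about 6 points at 0.3 (A: 68.1 v 61.9%; B: 78.7 v 72.7%) and 13 to 15 points at 0.5 (B: 87.4 v 74.3%; A: 76.3 v 61.7%).

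**5. The adjusted alternative.** In A, a proportional-odds model adjusted for age and gender had power 75.4, 77.4, 77.9 and 80.5%, against 74.3, 75.1, 74.5 and 74.8% unadjusted: a gain of 1.1 to 5.7 points. Its likelihood-ratio test had type I error of 5.6 to 6.0%, so part of that gain is not real. It also needs ordered categories, which the protocol does not state.

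**6. The one result with usable counts.** Section 1.2.20 reports bulging in 11 eTEP participants and no controls. Assume all 30 per group were assessed.

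- Fisher: p = 2 × C(30,11)/C(60,11) = 0.0003.
- Exact McNemar: with no control events, all 11 affected pairs are discordant in one direction, so p = 2 × 0.5^11 = 0.0010.

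Both agree with the significance the protocol reports. This is a 2 x 2 table, so it illustrates the point and does not test the 3 x 2 analyses.

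**The case for a change.** The strongest case for a finding is that it does not rest on silence. Section 3.1.9 records, in the past tense, that an independent-samples test was run after individually matched selection, and no later analysis plan can make that test use the pairs. If one of the non-significant comparisons in 1.2.20 came from such a table, a conservative test bears on how it is read, and naming the variables would be cheap.

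The facts in this argument stand: the matching is individual, Fisher's test ignores it, and the direction is conservative for non-negative correlation. What fails is the step from there to an error. The protocol ties no reported comparison to a 3 x 2 table. At the correlation that gender and age can plausibly produce, a paired test is as likely to lose power as to gain it. Which variables go into which test is detail that a protocol commonly leaves to the analysis plan.

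One limit applies to the reassurance. Type I error below 5% assumes close age matching, and 1.2.12 gives nearest age without a caliper. In a simulation with age and gender explaining 20% of outcome variance, Fisher's null rejection rate was 3.5% with no group age gap, below 5% at a gap of 0.25 SD, 5.3% at 0.5 SD and 7.9% at 0.75 SD. The protocol gives no ages, so such gaps cannot be excluded, though the matching rule is meant to prevent them. A paired test would not remove such a gap either, because it enters every pair difference.

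**Conclusion.** The concern does not hold. Section 3.1.9 names Fisher's test in a list of software and ties it to no variable, so no outcome is shown to be analysed against the design. If the tables do hold outcomes, the test is valid under close matching. Its power differs from that of the paired alternative by about 3 points in either direction for r from 0 to 0.2. Statisticians may reasonably differ on that choice.

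This rests on three assumptions: a weak, non-negative within-pair correlation, no large residual age gap, and a two-sided 5% level. At r near 0.5 the loss would be 13 to 15 points, but matching on gender and age alone is unlikely to produce that. Nothing is concluded here about the unnamed JASP tests or the primary outcomes.

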3.1.10 Methods: Data monitoring

A specific data monitoring committee other than the primary sponsor was deemed irrelevant given the observational nature of the study. Interim results will only be available to the primary sponsor. No specific stopping guidelines are in effect.

Adverse events are part of the secondary outcomes (1.2.17) and will be given within the final report. Unintended events will also be reported within the final manuscript.

Auditing of intended trial conduct was assessed at ethics review during the meeting of "Commissie voor Ethiek" at AZ Alma on June 8, 2022. No further auditing is intended.

